2. STUDY OBJECTIVES AND STUDY DESIGN

2.1. Objectives

Primary

To monitor the occurrence of malignancy in pediatric subjects with eoJIA, ERA, or PsA.

Secondary

- *To assess the long-term safety profile of etanercept;*
- *To evaluate the long-term effect of etanercept on clinical benefit and physical function.*

CCI [REDACTED]

[REDACTED]

[REDACTED]

2.2. Study Design

2.2.1. Basic Features of the Study Design

This is an open-label, single treatment, multi-center, 8-year extension study in pediatric subjects who have been diagnosed with one of 3 subtypes of JIA (eoJIA, ERA, or PsA), have received at least one dose of etanercept and completed approximately 96 weeks of participation in study 0881A1-3338-WW (B1801014). These subjects will be asked to participate in study B1801023. It is anticipated that approximately 100 subjects will be enrolled in study B1801023. This 96-month study contains 3 periods: an active treatment period, a withdrawal/re-treatment period, and an observational period.

Active treatment period

Subjects who completed approximately 96 weeks of active treatment with investigational product (etanercept) in study 0881A1-3338-WW (B1801014) and are eligible to continue investigational product in study B1801023 will enter directly into the active treatment period. These subjects may continue to receive investigational product for up to 8 additional years (96 months).

Withdrawal/Re-treatment period

Withdrawal: Subjects who have either completed approximately 96 weeks of treatment in study 0881A-3338 or were enrolled in the active treatment period of study B1801023 and who have either met the Wallace definition for clinically inactive disease for at least 6 months on investigational product (etanercept) or who, in the investigators judgment, have had a good clinical response and would benefit from withdrawal from investigational product and are otherwise eligible can enter the withdrawal/re-treatment period. However, the withdrawal/re-treatment period is optional and it is ultimately up to the investigator and subject to determine when the subject should be withdrawn from treatment.

Re-treatment: Subjects requiring re-treatment per the investigator's clinical judgment and who are otherwise eligible will be offered the option to re-start treatment with investigational product.

Subjects may not enter the withdrawal/re-treatment period more than once during the study.

Observational period

All subjects will be followed for a total of 8 years from the time of initial entry into the study as follows:

Subjects who discontinue investigational product prior to completing 96 weeks of active treatment in study 0881A1-3338-WW (B1801014) for any reason or who are not eligible to continue investigational product in study B1801023 will not be permitted to re-start investigational product in study B1801023 and will be asked to enter the observational period. Subjects who participate in the active treatment period of study B1801023 and subsequently discontinue use of investigational product at any time before completion of the study and do not participate in the withdrawal/re-treatment period for any reason (i.e., ineligible or subject declined participation) will be asked to participate in the observational period. Subjects who participate in the withdrawal period and are ineligible for re-treatment with investigational product for any reason will be asked to participate in the observational period. Subjects who participate in the re-treatment period and subsequently discontinue investigational product prior to the completion of the study will be asked to participate in the observational period.

Once a subject enters into the observational period, he or she cannot resume investigational product for the remaining time in the study. Subjects participating in the observational period of study B1801023 may receive standard of care including any anti-TNF agents (eg, commercial etanercept) and/or other biologic agents for treatment of their disease at the discretion of the investigator.

2.2.2. Interim Analysis

No formal statistical interim analyses are planned. However, a descriptive analysis will be performed at a minimum of every 2 years based on the time of last patient first visit. In addition, summaries of safety and efficacy assessments will be produced at intervals to satisfy regulatory obligations and the requirements of the Internal Review Committee.

2.2.3. Sample Size Rationale

The sample size for this safety extension protocol, as agreed upon with regulatory authorities, is not based on efficacy considerations; rather, all eligible subjects who either complete or discontinue from study 0881A1-3338-WW (B1801014) will be asked to participate in study B1801023. The anticipated enrollment is approximately 100 subjects.

3.2. Withdrawal Analysis Set

The withdrawal analysis set (WAS) will include those subjects who entered the withdrawal period. Only data collected in the withdrawal period will be included.

3.3. Re-treatment Analysis Set

The re-treatment analysis set (RTAS) will include those subjects who entered the re-treatment period. Only data collected in the re-treatment period will be included.

4. SPECIFICATION OF ENDPOINTS AND VARIABLES

The primary endpoints in this study are related to safety. Efficacy endpoints are secondary.

4.1. Demography and Baseline Characteristics

The demographic data include age, sex, race, weight, height and BMI. The baseline characteristics are: subtype of JIA, disease duration, number of prior DMARDS, use of the following medications: DMARDS, methotrexate, HCQ, chloroquine, SSZ, oral corticosteroids and oral NSAIDS.

4.2. Endpoints**4.2.1. Primary**

The occurrence of malignancy is the primary endpoint for all subjects.

4.2.2. Secondary Endpoints

The secondary endpoints include

- *the occurrence of serious adverse events (SAE, infectious and non-infectious events will be summarized separately),*
- *the occurrence of medically important infections (ie, an infection requiring hospitalization and /or parenteral [intravenous (IV), intra-muscular (IM)] anti-infective agents).*
- Hospitalization: For any hospitalizations, the admission date, discharge date and reason for hospitalization will be collected during the study.
- Death: For any deaths, date of death and cause of death will be collected during the study.

- Nonstudy medication: nonstudy medications are coded using the WHO Drug Dictionary (2006 Q3). The Prior, Concomitant, After (PCA) flag for nonstudy medications will be derived for both parent study and extension study (only for active treatment period):
 - Prior nonstudy medications are defined as any nonstudy medications taken before the first dose of investigational product taken at the start of the study,
 - Concomitant nonstudy medications are defined as any nonstudy medications taken during the treatment period (from the first dose to the last dose of the investigational product).
 - After nonstudy medications refer to any nonstudy medications taken after the last dose of the investigational product.(not applicable for observational period)
- Exposure: the total number of doses taken and exposure time.

The above endpoints will be collected for all subjects. The following endpoints will be collected only for subjects in the active treatment period, or withdrawal/re-treatment period in the extension study:

Non-serious adverse Events (Adverse events that occur up to 30 days after the last dose of investigational product will be counted as having occurred during the treatment period) This is applied for active and retreatment periods. If an AE started in active or retreatment period and continued into withdrawal or observational period, it will be only counted in active or retreatment period, it will not be counted in withdrawal or observational period again. If an event started in withdrawal or observational period, and after 30 days of the last dose of investigational product of active period or re-treatment period, this event will not be counted.

Occurrence of withdrawals from investigational product due to adverse events;

Laboratory evaluations (ie, hematology, blood chemistry, and CRP)

Tanner Stage Assessment for subjects <18 years of age or who have a score of <5 on 1 or more applicable domain(s). The Tanner Assessment does not need to be repeated if it was performed within 2 months before the early withdrawal visit.

Vital Signs: Temperature, blood pressure (mmHg) and pulse rate (beats/min, after sitting for at least 5 minutes);

Growth parameters: height, weight, BMI;

- Efficacy:
 - *ACR Pediatric 30, 50, 70, 90, and 100, defined as $\geq 30\%$ (and 50%, 70%, 90%, 100%, respectively) improvement from baseline in at least 3 of the 6 following variables, with no more than 1 of the remaining variables worsening by $> 30\%$:*
 - *Physician's Global Assessment (PGA) of Disease Activity on a 21-circle visual analogue scale (VAS);*
 - *Patient/Parent Global Assessment on a 21-circle VAS;*
 - *Childhood Health Assessment Questionnaire (CHAQ)*

- *Number of joints with active arthritis, defined as joints that are swollen or, in the absence of swelling, joints with limited range of motion accompanied by pain and/or tenderness;*
- *Number of joints with limited range of motion;*
- *Laboratory measure of inflammation, c-reactive protein (CRP);*

(Note: ACRPedi responses will be calculated based on parent study baseline. For subjects aged ≥ 18 years, CHAQ is missing)

- *Individual components of the ACR Pediatric Assessments;*
- *Pain Assessment on a 21-circle VAS;*
- *Duration of morning stiffness in minutes;*
- *Clinically inactive disease defined as follows per 2011 Wallace Criteria:*
 - *No joints with active arthritis (defined as joints that are swollen or, in the absence of swelling, joints with limited range of motion accompanied by pain and/or tenderness);*
 - *No fever, rash, serositis, splenomegaly, or generalized lymphadenopathy attributable to JIA;*
 - *No active uveitis;*
 - *CRP level within normal limits in the laboratory where tested or, if elevated, not attributable to JIA;*
 - *PGA of disease activity score of best possible on the scale used;*
 - *Duration of morning stiffness of ≤ 15 minutes;*
- *The Juvenile Arthritis Disease Activity Score (JADAS), using 4 components (PGA of Disease Activity, Patient/Parent Global Assessment, number of joints with active arthritis and CRP).*

- *Additional Secondary Endpoints for ERA Subjects*
 - *Overall Back Pain and Nocturnal Back Pain on a 100 mm VAS;*
 - *Bath Ankylosing Spondylitis Metrology Index (BASMI) components (Intermalleolar Distance, Cervical Rotation, Modified Schober's Test, Lateral Flexion, and Tragus to Wall Distance. Note: Modified Schober's Test is used for BASMI calculation. Schober's Test, not Modified Schober's Test, was collected for this study. So BASMI cannot be calculated for this study).*
- *Additional Secondary Endpoints for PsA Subjects*
 - *Body Surface Area (BSA);*
 - *PGA of Psoriasis.*
- *Health outcomes assessments for Subjects in the Active Treatment Period, and Withdrawal/Re-treatment Period:*
 - *Childhood Health Assessment Questionnaire (CHAQ): for subjects aged <18 years at the time of assessment;*
 - *Health Assessment Questionnaire (HAQ): for subjects aged ≥18 years at the time of assessment.*
 - *Proportion of subjects with total CHAQ score improvement of >0.188 (decrease by >0.188) from baseline of 1014.*

█ [REDACTED]

█ [REDACTED]

█ [REDACTED]

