8.7. Severity Assessment

If required on the adverse event case report forms, the investigator will use the adjectives MILD, MODERATE, or SEVERE to describe the maximum intensity of the adverse event. For purposes of consistency, these intensity grades are defined as follows:

MILD	Does not interfere with subject's usual function.
MODERATE	Interferes to some extent with subject's usual function.
SEVERE	Interferes significantly with subject's usual function.

Note the distinction between the severity and the seriousness of an adverse event. A severe event is not necessarily a serious event. For example, a headache may be severe (interferes

significantly with subject's usual function) but would not be classified as serious unless it met one of the criteria for serious adverse events, listed above.

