5.2. Treatment-emergent Events

An event is defined as a treatment-emergent event if the event occurred during the active period (either parent or extension studies) or re-treatment period with onset dates between the first dose date of investigational product and within 30 days after the last dose of investigational product. If a treatment-emergent event started in active or re-treatment period and continued to withdrawal or observational period, it will be only counted in active or re-treatment period, it will not be counted in withdrawal or observational period again. If an event started in the withdrawal or observational periods, and after 30 days of the last dose of investigational product of the active period or re-treatment period, this event is not a treatment-emergent event.

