5.5. Malignancies, SAE and Medically Important Infections

The malignancies, serious adverse events and medically important infections will be summarized using the frequency and percentage of subjects reporting events. The adjusted rate per 100 subject-years of exposure to etanercept (defined as # of events/total exposure*100) will be summarized also.

The incidence of malignancies may be compared to external data sources to generate standardized incidence ratios (SIRs) to aid interpretation.

In addition to showing cumulative rates over the entire study period (including both parent study and extension), incidences of subjects with malignancies, serious adverse events and medically important infections as well as exposure-adjusted rates will also be categorized by year for each year from 1 through 10.

These summaries and analyses will be performed for:

- FAS, all events in all periods;
- FAS, treatment-emergent events in the on-drug period (active and retreatment periods together).

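### Onset-only classification leaves an event that begins in the withdrawal period and worsens or becomes serious after etanercept is restarted out of the on-drug safety tables

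*SAP*

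**What the plan says.** SAP 5.2 calls an event treatment-emergent if it occurs in the active or re-treatment period "with onset dates between the first dose date of investigational product and within 30 days after the last dose of investigational product". It then deals with events that begin off drug: "If an event started in the withdrawal or observational periods, and after 30 days of the last dose of investigational product" of the active or re-treatment period, "this event is not a treatment-emergent event". No exception is made for later worsening or seriousness.

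SAP 4.2.2 carries the same rule under non-serious adverse events. It gives a 30-day window ("Adverse events that occur up to 30 days after the last dose of investigational product will be counted as having occurred during the treatment period") and a carry-over sentence for events that run from on drug to off drug ("If an AE started in active or retreatment period and continued into withdrawal or observational period"). For events that start off drug beyond the window it says "this event will not be counted". The carry-over sentence is about the opposite direction from the one at issue here. The operative text is the sentence that follows it and, for serious events, SAP 5.2.

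SAP 5.5 summarises malignancies, serious adverse events and medically important infections twice: once for all events in all periods, and once for "FAS, treatment-emergent events in the on-drug period (active and retreatment periods together"). SAP 5.6 summarises general adverse events for treatment-emergent on-drug events and for the withdrawal analysis set (WAS). It asks for no adverse event summary in the re-treatment analysis set.

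On recording, Protocol 8.7 has the investigator grade each event "to describe the maximum intensity of the adverse event", where the case report form asks for it.

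**The concern.** The design provides a planned path from off drug back to on drug. A subject in the withdrawal period who relapses may restart etanercept (Protocol 3 and 6.1.5). An event can be open at that moment. Worsening of the underlying disease is itself listed as an adverse event (Protocol 8.3). Active tuberculosis is the only infection named among the additional re-treatment exclusions (Protocol 4.2.3.1), so a minor infection does not automatically prevent restart.

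If such an event becomes more severe, or first meets the serious or medically-important-infection definition after restart, the clinically relevant change happened on drug. The onset rule still places it off drug. Re-treatment is where an effect of re-exposure on existing conditions would show, and the on-drug tables are where a reader would look for it. From this gap alone, the on-drug count can only come out too low.

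**Working it through.** The plan states no figure that depends on this rule, so there is nothing to reproduce. The check is to apply the rule to test cases and then to size one misplaced event.

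**Step 1: the rule.** For a dosing period from day *a* to day *b*, SAP 5.2 makes an event on-drug if *a* ≤ onset ≤ *b* + 30. The amended rule also makes it on-drug if the date of worsening or of first seriousness falls in the same window.

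Hypothetical subject: active dosing from day −700 to day 0, re-treatment from day 200 to day 600. The on-drug windows are −700 to 30 and 200 to 630.

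| Event | SAP 5.2 as written | With a clause on change |
|---|---|---|
| Starts day 20, serious day 240 | on-drug (20 ≤ 30) | on-drug |
| Starts day 120, serious day 240 | **not on-drug** (30 < 120 < 200) | **on-drug** (200 ≤ 240 ≤ 630) |
| Starts day 120, no change | not on-drug | not on-drug |
| Starts day 240 | on-drug | on-drug |
| Starts day −10, continues off drug | on-drug | on-drug |

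Only the second case differs. It needs all three of: onset in the withdrawal period, onset more than 30 days after the last dose, and a change after restart.

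**Step 2: who can be affected.** Subjects in the observational period cannot resume investigational product (Protocol 3), and the withdrawal/re-treatment period can be entered once. The gap therefore concerns only subjects who move from withdrawal to re-treatment. The documents do not give their number.

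**Step 3: where the event is reported.** The second case would appear in the all-periods table of SAP 5.5. If the subject was hospitalised or died, it would also appear in the listings of SAP 5.13 or 5.14. An event that worsened without becoming serious would appear only in the WAS summary of SAP 5.6. None of these outputs assigns the change to re-treatment.

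**Step 4: size.** SAP 5.5 defines the adjusted rate as events divided by total exposure, times 100. One additional event therefore adds 100/E per 100 subject-years, where E is on-drug exposure in subject-years. SAP 5.5 and 5.6 pool the active and re-treatment periods, including the parent study. E is not stated, so these values are assumed:

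- E = 500: 100/500 = 0.2
- E = 1,000: 100/1,000 = 0.1

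For orientation, 100 subjects treated for all 10 years would give 100 × 10 = 1,000 subject-years.

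The by-year rates in SAP 5.5 and 5.6 are more sensitive. With about 100 subjects in the extension, one extension year holds at most about 100 on-drug subject-years, so one event adds at least about 100/100 = 1.0 per 100 in that year.

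**The case against.** The strongest reply is that the events that matter most are not lost. Malignancies (the primary endpoint), serious events and medically important infections are all counted in the all-periods table, cumulatively and by year. Admission dates are collected, and potentially important laboratory values are summarised separately for the re-treatment set (SAP 5.7). That stands. A reader might infer that these events drop out of the safety report altogether, and the documents do not support that. They drop out of the on-drug tables.

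Second, a reader might infer that the protocol prevents a worsening from being recorded as a new event. It does not. Protocol 8.3 lists worsening of underlying disease and changes in physical examination findings as adverse events. Protocol 8.7 is a grading rule that applies only if the form asks for severity. Sites may open a new record with its own onset date, which would close the gap for that event. But neither document requires it, and no form-completion instructions are among them.

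Third, the infection route is narrower than it first looks. The investigator can exclude a subject with a severe acute condition (Protocol 4.2.3.1), and a medically important infection during withdrawal requires consultation with the sponsor on whether re-treatment is allowed (Protocol 6.3). An infection that is minor at restart remains possible. Its frequency is unknown.

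Fourth, a large bias is tempting to infer. Suppose 20 subjects restart with 0.5 to 1 open event each, and 10% to 30% of those events worsen. That gives 20 × 0.5 × 0.10 = 1 to 20 × 1 × 0.30 = 6 events, or 1.7 to 10 per 100 over 60 subject-years of re-treatment. Every input is assumed, and SAP 5.5 and 5.6 specify no re-treatment-only adverse event rate. Over a pooled 500 subject-years the same events give 0.2 to 1.2 per 100.

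Finally, a clause on worsening could count one episode twice, in WAS and on drug. That is a fair criticism of an incomplete remedy, and the fix has to settle it.

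**Conclusion.** The point holds in a limited form. SAP 5.2 states a rule that assigns to off-drug time an event whose worsening or first seriousness occurred on re-treatment, and no other provision in the documents corrects the assignment. It applies only to onset more than 30 days after the last dose, in subjects who go from withdrawal to re-treatment.

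The count of malignancies over all periods, which serves the primary objective, is not affected. What suffers is the on-drug part of the secondary long-term safety objective. The effect on the pooled on-drug rate is probably small: 0.1 to 0.2 per 100 subject-years for each such event, if pooled exposure lies between 500 and 1,000 subject-years. The number of such events cannot be derived from the documents.

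A side effect is possible but not established. If one record carries a maximum grade reached after restart, the WAS severity summary could show that grade as off-drug, although SAP 3.2 limits WAS to data collected in the withdrawal period.

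**What to change.** In SAP 5.2, and in 4.2.2 for non-serious events, add a clause. An event that is not treatment-emergent by onset also counts as treatment-emergent if it increases in severity, or first meets the serious or medically-important-infection criteria, between the first re-treatment dose and 30 days after the last dose. Attribute it to on-drug time, and to a study year, by the date of that change.

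Capture that date through a new adverse event record linked to the original one, or through a date-of-change field. For hospitalised events, use the admission date that SAP 4.2.2 already collects.

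State the counting rule: the grade before restart stays in WAS, the worsened grade counts on drug, and the all-periods table counts the linked episode once.

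The cost is one clause in two SAP sections, a short form-completion instruction and a slightly higher on-drug event count. Changes that happened before the instruction takes effect can be dated only where a date such as hospital admission exists. The report should say so.

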2.2.2. Secondary Endpoints for Subjects in the Observational Period

- Occurrence of serious adverse events, including serious infections;
- Occurrence of medically important infections (ie, an infection requiring hospitalization and /or parenteral [intravenous (IV), intra-muscular (IM)] anti-infective agents).

2.2.3. Secondary Endpoints for Subjects in the Active Treatment Period, and Withdrawal/Re-treatment Period

- Occurrence of serious adverse events, including serious infections;
- Occurrence of medically important infections (ie, an infection requiring hospitalization and /or parenteral [intravenous (IV), intra-muscular (IM)] anti-infective agents);

- Occurrence of all adverse events, including infections, infections considered preventable by vaccination, and injection site reactions;
- Occurrence of withdrawals from investigational product due to adverse events;
- Laboratory evaluations;
- Growth parameters;
- Tanner Stage Assessment for selected subjects;
- ACR Pediatric 30, 50, 70, 90, and 100, defined as $\geq 30\%$ (and 50%, 70%, 90%, 100%, respectively) improvement from baseline in at least 3 of the 6 following variables, with no more than 1 of the remaining variables worsening by $> 30\%$:
 - Physician's Global Assessment (PGA) of Disease Activity on a 21-circle visual analogue scale (VAS);
 - Patient/Parent Global Assessment on a 21-circle VAS;
 - Childhood Health Assessment Questionnaire (CHAQ)/Health Assessment Questionnaire (HAQ);
 - Number of joints with active arthritis, defined as joints that are swollen or, in the absence of swelling, joints with limited range of motion accompanied by pain and/or tenderness;
 - Number of joints with limited range of motion;
 - Laboratory measure of inflammation, c-reactive protein (CRP);
- Individual components of the ACR Pediatric Assessments;
- Pain Assessment on a 21-circle VAS;
- Duration of morning stiffness in minutes;
- Clinically inactive disease defined as follows per Wallace Criteria:¹²
 - No joints with active arthritis (defined as joints that are swollen or, in the absence of swelling, joints with limited range of motion accompanied by pain and/or tenderness);
 - No fever, rash, serositis, splenomegaly, or generalized lymphadenopathy attributable to JIA;
 - No active uveitis;

- CRP level within normal limits in the laboratory where tested or, if elevated, not attributable to JIA;
- PGA of disease activity score of best possible on the scale used;

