5.6. General Adverse Events

The occurrence of all treatment-emergent adverse events (excluding infection and ISR), infections, infections considered preventable by vaccination, and injection site reactions will be separately summarized by incidence rate (proportion of subjects reporting events) and adjusted rate per 100 subject-years of exposure to etanercept. Adverse events will also be summarized by severity and relationship to investigational product. Adverse events occurring in >1 subject in any of the subtypes may be summarized as well.

- Tabulations of withdrawals from investigational product due to adverse events will be provided.
- In addition to showing cumulative rates over the entire study period (including both parent study and extension), incidences of subjects with treatment-emergent event as well as exposure-adjusted event rates will also be categorized by year for each year from 1 through 10.

These summaries will be performed for FAS (treatment-emergent events in on-drug period (active and retreatment periods together)) and WAS.

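### SAP 4.2.2, 5.2 and 5.6 conflict on whether non-serious adverse events that start in the withdrawal period more than 30 days after the last dose are reported

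*SAP*

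**What the plan says.** **SAP 4.2.2**, under the item "Non-serious adverse Events", gives three counting rules.

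- Near the last dose: "Adverse events that occur up to 30 days after the last dose of investigational product will be counted as having occurred during the treatment period".
- Carried over from the active or re-treatment period: the event is counted there, and "it will not be counted in withdrawal or observational period again".
- Late onset in withdrawal or observation: "after 30 days of the last dose of investigational product of active period or re-treatment period, this event will not be counted".

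**SAP 5.2** gives a parallel rule. It begins "If an event started in the withdrawal or observational periods, and after 30 days of the last dose of investigational product" and ends by classing the event as not treatment-emergent. It does not say that the event goes uncounted.

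**SAP 5.6** opens by describing summaries of treatment-emergent adverse events, together with infections, vaccine-preventable infections and injection site reactions. Rates are per 100 subject-years of etanercept exposure. It then says: "These summaries will be performed for FAS (treatment-emergent events in on-drug period (active and retreatment periods together)) and WAS". **SAP 3.2** defines WAS as the subjects who entered withdrawal: "Only data collected in the withdrawal period will be included".

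**Protocol 2.2.3** lists, as a secondary endpoint for the active and withdrawal/re-treatment periods, "Occurrence of all adverse events, including infections, infections considered preventable by vaccination, and injection site reactions". Protocol 8.2 has all adverse events, serious and non-serious, recorded throughout the withdrawal/re-treatment period. Protocol 9.4.2 asks for a summary of all adverse events as well as the treatment-emergent ones.

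**The concern.** The SAP plans an adverse-event summary for the withdrawal set, but its own counting rules, taken at their word, assign no non-serious event to that summary. A programmer has to override one section to follow another. Two competent programmers could produce an empty WAS table and a full one from the same plan.

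Withdrawal is the only period off investigational product in which sites collect non-serious adverse events generally. Direct and later entrants to the observational period are followed only for serious events, malignancies and medically important infections. Protocol 8.3 counts worsening of the underlying disease, and symptoms resulting from stopping a drug, among possible adverse events. Events of that kind may well start after day 30. An empty or nearly empty table could be misread as few events off drug.

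**Working it through.** The plan states no figure on this point, so the check is a classification of events followed by a simple time share.

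**Step 1. Classify each possible onset of a non-serious event in a withdrawal subject.**

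| Onset | SAP 4.2.2, literally | SAP 5.2 | Left for WAS? |
|---|---|---|---|
| Before withdrawal, continuing into it | active or re-treatment period only | treatment-emergent | No |
| In withdrawal, up to 30 days after last dose | treatment period | treatment-emergent | No |
| In withdrawal, more than 30 days after last dose | not counted | not treatment-emergent | No under 4.2.2; open under 5.2 |

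The first two rows are settled and avoid double counting. Only the third row could fill a WAS table. SAP 4.2.2 closes it, 5.2 leaves it open, and 5.6 points both ways: the lead sentence is about treatment-emergent events, but the population sentence ties that restriction to FAS and then adds WAS.

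**Step 2. Find what is unaffected.**

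- Malignancies, serious events and medically important infections are summarised for FAS over all events in all periods (SAP 5.5).
- Laboratory data, vital signs and Tanner scores (SAP 5.7) and growth (SAP 5.8) are summarised for WAS.
- Hospitalizations and deaths are listed for FAS (SAP 5.13 and 5.14).

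The gap is therefore non-serious events that are neither malignancies nor medically important infections. It includes non-serious infections that fall short of medically important.

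**Step 3. Find the share of follow-up time in the third row.**

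Inputs: the 30-day window (SAP 4.2.2) and a maximum of 96 months from study baseline (Protocol 6.1.2.2), which is 8 × 365.25 = 2,922 days. The other lengths are assumptions. Six months is illustrative: Protocol 1.2 cites a retrospective chart review of 26 patients with a 50% probability of being symptom-free at that point.

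Formula: share = 1 − 30/D, with D in days from the last dose.

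| Assumed length | D (days) | 30/D | Share after day 30 |
|---|---|---|---|
| 6 months | 182.6 | 16.4% | 83.6% |
| 1 year | 365.25 | 8.2% | 91.8% |
| 2 years | 730.5 | 4.1% | 95.9% |
| 8 years (maximum) | 2,922 | 1.0% | 99.0% |

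**The case against.** The strongest reply is that a late event going uncounted means only that it is not counted as on-treatment. Several things support this. The sentence sits in a passage about attribution to the active and re-treatment periods. The rule just before it says a carried-over event is not counted in withdrawal a second time, which presupposes a withdrawal count. SAP 5.2 uses the language of classification. SAP 5.6 attaches its on-drug restriction to FAS alone, and listing WAS there would be pointless if nothing could enter it.

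This reading is plausible and probably what was intended, so a reader who infers that the WAS table is certain to be empty goes further than the text allows. It does not remove the conflict. The disputed sentence names no period to which the exclusion is confined, whereas the sentence before it does. The lead sentence of 5.6 and its by-year bullet also stay with treatment-emergent events.

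Two other replies have force. Protocol 9 lets the SAP modify the protocol's analysis plans, so departing from 9.4.2 is not in itself an error. But nothing in the SAP announces a decision to drop these events, and 5.6 suggests the opposite. Second, withdrawal entrants are selected for inactive disease or good response, neither document prespecifies an on-drug versus off-drug comparison, and SAP 5.11 allows for commercial etanercept in this period. It would be wrong to say that the study loses a clean internal control. What is at stake is a descriptive account.

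**Conclusion.** The conflict is real and limited. On the literal text, no non-serious adverse event remains for the WAS summary that SAP 5.6 plans, contrary to Protocol 2.2.3 and 9.4.2. On the alternative reading the table is populated, but the SAP does not say so.

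A reader might infer that safety off drug goes unreported. The documents do not support that: the primary endpoint, serious events and medically important infections are summarised in every period, and the other safety measures are summarised for WAS or listed.

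Nor do the figures of about 84% to 99% mean that this share of events is lost. They are shares of follow-up time, measured from the last dose, at assumed lengths, and no onset distribution is available. The upper figure applies only to a subject who enters withdrawal directly at baseline and never leaves it.

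Severity is moderate: one descriptive secondary safety table is affected, no hypothesis test depends on it, and the data are collected either way.

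**What to change.** 1. In SAP 4.2.2, replace the end of the disputed sentence with: *the event is excluded from the treatment-emergent (on-drug) count; if its onset falls in the withdrawal period, it enters the WAS summaries.*
2. In SAP 5.6, state that the WAS summaries use all adverse events with onset in the withdrawal period more than 30 days after the last dose, and that only the FAS on-drug summaries are restricted to treatment-emergent events.
3. In SAP 5.6, give WAS its own denominator: withdrawal-period person-time starting 30 days after the last dose, in place of etanercept exposure. Without this, the added events have no matching time at risk and the rate column cannot be interpreted. Label it as time off investigational product, since SAP 5.11 allows for commercial etanercept in this period.

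The cost is a few sentences of SAP text and one derived person-time variable. No new data are needed. No event is counted twice, because the on-drug and WAS counts divide at day 30.
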